Subjects who prematurely discontinue treatment during the transplantation phase should return for a Treatment Discontinuation Visit and undergo the study procedures as outlined in Tables [5](#) and [6](#).

In Arm 1, 30 candidates will undergo kidney transplantation with kidneys from HCV RNA-positive donors. After n=30 kidney transplantation events from HCV RNA-positive donors have occurred, no further subjects will be enrolled into the study. Already enrolled subjects who receive an HCV RNA-positive donor kidney offer that meets study criteria and are scheduled to be transplanted within 24 hours after the 30th kidney transplant from an HCV RNA-positive donor will also be allowed into treatment arm A of the study.

Patients enrolled in the trial will be notified by phone that the HCV RNA-positive arm of the trial has completed enrollment and remaining subjects (now in Arm 2) will have the ability to accept (i) a study-eligible kidney from an HCV RNA-negative/HCV Ab-positive donor up until 24 weeks after the last kidney transplant event from a study-eligible HCV RNA-positive donor, (ii) a standard of care kidney transplant, or remain on the waiting list for the duration of the study. G/P treatment, if needed, will be provided free of charge to a subject in Arm 2A who developed HCV viremia after up to 24 weeks post-transplant of a kidney from an HCV RNA-negative/HCV Ab-positive donor.

5.1.5.1 G/P treatment phase/Visits and laboratory evaluations after transplantation for subjects who receive a study eligible HCV RNA-positive kidney in Arm 1

Visit 1: Peri-transplant visit

The treating physician will evaluate the patient's overall condition and make a judgment on whether transplantation is safe. The following recipient-donor-kidney match results exclude transplantation in this protocol: a) Blood group incompatibility between donor and recipient; b) Cross match reactivity, or clinically meaningful donor specific antibody, or other immunological reactivity related to an allograft offer deemed a substantial risk for rejection by the responsible investigator.

The following research procedures and activities will be performed:

- Obtain medication data
- Donor blood sample (if available)
- Assessment of recipient and donor-kidney match for exclusion from transplantation in this protocol

Visit 2: Post-kidney transplant (Day 3 ± 1 day)

The study staff will meet the subject in their hospital room, three days after their kidney transplant.

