6.1.1.2 Serious Adverse Events

If an adverse event meets any of the following criteria, it is to be reported to the sponsor as a SAE within 24 hours of the site being made aware of the serious adverse event:

Death of Subject	An event that results in the death of a subject.
Life-Threatening	An event that, in the opinion of the investigator, would have resulted in immediate fatality if medical intervention had not been taken. This does not include an event that would have been fatal if it had occurred in a more severe form.
Hospitalization or Prolongation of Hospitalization	An event that results in an admission to the hospital for any length of time or prolongs the subject's hospital stay. This does not include an emergency room visit or admission to an outpatient facility.
Congenital Anomaly	An anomaly detected at or after birth, or any anomaly that results in fetal loss.
Persistent or Significant Disability/Incapacity	An event that results in a condition that substantially interferes with the activities of daily living of a study subject. Disability is not intended to include experiences of relatively minor medical significance such as headache, nausea, vomiting, diarrhea, influenza, and accidental trauma (e.g., sprained ankle).
Important Medical Event Requiring Medical or Surgical Intervention to Prevent Serious Outcome	An important medical event that may not be immediately life-threatening or result in death or hospitalization, but based on medical judgment may jeopardize the subject and may require medical or surgical intervention to prevent any

of the outcomes listed above (i.e., death of subject, life-threatening, hospitalization, prolongation of hospitalization, congenital anomaly, or persistent or significant disability/incapacity). Additionally, any elective or spontaneous abortion or stillbirth is considered an important medical event. Examples of such events include allergic bronchospasm requiring intensive treatment in an emergency room or at home, blood dyscrasias or convulsions that do not result in inpatient hospitalization, or the development of drug dependency or drug abuse.

Note that criteria as described above apply to all SAEs that occur after consent for the trial. All SAEs in the trial will be categorized as pre-transplant vs post-transplant, as well as pre-study drug vs post study drug.

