9.4 Potential Risks and Benefits

9.4.1 Risks of Study Procedures

There are several areas of potential risk in this study. We will obtain several blood samples from each subject. There is a risk of bruising, hematoma, and infection after phlebotomy, which are possible but not considered serious AEs. Fainting may occur, which is unlikely but considered a serious AE. The removal of <70 cc of blood every 1-4 weeks during the 40-week post-transplant period is a potential risk; however this amount is routinely taken from subjects for clinical indications without adverse effect. Study medications will be delayed until after phlebotomy on each study day.

Because we may store subjects' blood samples, there may be confidentiality risks associated with the storage and analysis of those samples or the information resulting from the analysis of those samples. Samples may be used for genetic testing. Under some circumstances, it can be a risk for genetic information to be known. To help ensure confidentiality, samples will be coded and stored in a secured facility. While situations

cannot be foreseen where potentially sensitive genetic information is revealed or where people who should not have this information could obtain it (representing a loss of confidentiality), however, it is possible that presently unforeseen situations may arise where this could happen.

The risk of undergoing screening includes potential identification of new health problems that subjects were unaware of. If we discover new health problems, we will answer subjects' questions and try to arrange appropriate treatment if any is needed. If new health problems are discovered, it is possible that subjects would not be able to enter this study. It is also possible that subjects would no longer be eligible for kidney transplantation based on the results.

The risks associated with a Fibroscan are that the probe used on the abdomen during the Fibroscan may lead to mild soreness in the area for about a day.

The risks of any kidney transplant surgery include blood loss, infections, and deep vein thrombosis. There are also risks related to immunosuppression and standard anti-infective therapy. The risks of any kidney transplant also include primary graft non-function, delayed graft function, acute rejection, and death. Re-admissions within 30 days after a kidney transplant are expected in approximately 40% of patients.

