Summary of Statistical Analysis Plan for MYTHIC Study

[Draft: April 26, 2020]

Part	Patient Group(s)	Outcome	Statistical Analysis ^a
1	Arm 1 (ITT)	SVR12	- estimated probability of SVR12 and 95% confidence interval (CI) - exact binomial calculations
2	Arm 1 (ITT)	Virologic failure (VF)	- estimated probability of SVR12 and 95% confidence interval (CI) - exact binomial calculations
3	Arm 1 (ITT)	Post-treatment virologic relapse	- estimated probability of SVR12 and 95% confidence interval (CI) - exact binomial calculations
4	All patients	HCV-viremic kidney transplant (KT); i.e., Arm 1 KT	- cumulative incidence and 95% CI - death and other KT types treated as competing risk - estimate non-parametrically, using Lin (1997) which proceeds through the cause-specific hazards, or Fan (2013) which uses Inverse Probability of Censoring Weighting (IPCW).
5	All patients	Non-HCV-viremic KT; i.e., Arm 2A-2B KT	- same as for component (4).
6	All, by Arm	Hospital admissions	- Arm treated as a time-dependent treatment - crude hospitalization rate per 100 patient-years (PY) and 95% CI - use robust variance estimator, to account for correlation among hospital admissions within-patient
7	All, by Arm	Hospital admissions	- Arm treated as a time-dependent treatment - proportional rates model (Lin et al., 2000) - robust SEs, to account for clustering within-patient
8(a)	All, and SRTR* controls	Kidney transplant	- exclude, from SRTR, all patients who indicated consent to receive an HCV-viremic KT (hereafter: SRTR*) - estimate prognostic score using SRTR* patients: KT as event - 1:5 matching (MYTHIC : SRTR*) based on prognostic score with caliper - Cox regression, with MYTHIC as lone covariate, stratified by matched set

8(b)	All, and SRTR* controls	Kidney transplant	Same as 9(a), but using exact matching on small set of predictors, with prognostic score used to break ties among potential matches
9	Arm 1 – ITT	Compliance	Treated as repeated binary (0/1) data, with 1 indicating compliance (i.e., having taken 80-120% of prescribed pills)
10	Arm 1 – ITT	Death	Time to event; Cox regression
11	Arm 1 – ITT	Graft failure	Time to event; Cox regression
12	Arm 1	Delayed graft function	DGF: binary (0/1) response. Compute OBS/EXP, where OBS=observed number of DGFs for Arm 1 and EXP= expected count based on logistic regression model fitted to HCV-negative UNOS patients from large academic centers

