13	Arm 1	Acute allograft rejection	AAR: Binary (0/1) response. Compute OBS/EXP, where OBS=observed number of AARs for Arm 1 and EXP= expected cunt based on logistic regression model fitted to HCV-negative UNOS patients from large academic centers
14	Arm 1	ALT elevation	Binary (0/1), with '1' corresponding to peak ALT > 5 x ULN, where ULN=upper limit of 'normal'.
15	All, by arm	Serious Adverse Event	SAE: recurrent event Arm treated as a time-dependent factor Proportional rates model, robust SEs to account for within-patient clustering
16	Arm 1, 2AB	eGFR	Repeated continuous response Linear mixed model, to account for clustering by patient
17	Arm 1, 2AB	Proteinuria	Binary response; logistic regression
18	Arm 1, 2AB	BK virus	Binary response; logistic regression

Notes:

a) Each of the above-listed analyses will be accompanied by appropriate summary statistics (e.g., mean, median, IQR, etc).

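### SAP Parts 7 and 15 fit one constant rate ratio per arm with no time-since-transplant term, so the Arm 1 versus 2A/2B ratio can mix risk with transplant timing; the crude Part 6 rates also depend on unequal follow-up

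*SAP*

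**What the plan says.** SAP Part 15 treats serious adverse events as recurrent events in all patients, by arm. It specifies "Arm treated as a time-dependent factor" and a "Proportional rates model, robust SEs to account for within-patient clustering". Part 7 applies the same type of model to hospital admissions, with "Arm treated as a time-dependent treatment". Part 6 summarises the same admissions as a "crude hospitalization rate per 100 patient-years (PY) and 95% CI". None of the three parts gives a time origin, a reference state, a time-since-transplant term or a check of proportionality.

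The protocol supplies the context:

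- **Early event level (Section 9.4.1):** "Re-admissions within 30 days after a kidney transplant are expected in approximately 40% of patients".
- **Admissions count as SAEs (Section 6.1.1.2),** apart from listed exceptions: "An event that results in an admission to the hospital for any length of time".
- **Follow-up after transplant:** 1 year in Arm 1 (Section 5.1). In Arms 2A and 2B it is the longer of 24 weeks after transplant and 1 year after enrolment (Sections 5.1 and 5.1.10).
- **Closure (Section 5.1.5):** "After n=30 kidney transplantation events from HCV RNA-positive donors have occurred, no further subjects will be enrolled into the study". Arm 2A transplants may continue for 24 weeks after the 30th Arm 1 transplant (Section 5.1), and some 2B categories are defined by falling after Arm 1 has closed (Section 4.2).

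**The concern.** A proportional rates model leaves the baseline rate free over its time axis and holds the ratio between arms constant. That works if the axis carries the main time trend in risk. Here the documented trend is time since transplant, but the model covers all patients, including Arm 2C, who have no transplant date, and arm changes at transplant. A single clock for such a model most naturally runs from enrolment.

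On that clock, take enrolment day 200. An Arm 1 patient transplanted on day 60 is then 140 days past surgery. An Arm 2 patient transplanted on day 190 is 10 days past surgery, inside the high-rate month. The model compares them as if they were at the same point in their course. If one arm tends to be transplanted sooner after enrolment, the arm ratio absorbs the difference.

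Safety is part of the primary objective (Section 4.1), and SAEs are a named post-transplant outcome for Arm 1 against 2A and 2B1-2B4 (Section 4.2, objective 3). A ratio that moves with transplant timing could hide or create a difference between viremic and other kidneys.

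**Working it through.** The documents state no rate, ratio or power for Parts 6, 7 or 15, so there is no figure of the plan's to reproduce. The check asks what the planned estimates converge to when true post-transplant risk is the same in both arms.

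**Inputs from the documents**
- Early rate: 40% readmitted in 30 days. As a constant hazard, -ln(0.60) = 0.511 events in 30 days, and 0.511 × 365.25/30 = 6.22 per patient-year. The simpler 0.40 × 365.25/30 gives 4.87.
- Follow-up rules as above.
- 30 Arm 1 transplants.

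**Assumptions (not in the documents)**
- Rate after day 30: 0.3, 0.5, 1.0 or 2.0 per year, with a flat 6.22 as control.
- Waitlist rate: 1.0 per year.
- 30 transplanted Arm 2 patients and 30 never transplanted.
- Transplant times uniform in the windows shown.

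**Parts 7 and 15, clock from enrolment.** Let W(t), A(t) and B(t) be the numbers waiting, post-transplant in Arm 1 and post-transplant in Arm 2 on enrolment day t, and let E_W, E_A and E_B be their expected events. The model solves

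- baseline(t) = [E_W(t) + E_A(t) + E_B(t)] / [W(t) + a·A(t) + b·B(t)]
- a = ΣE_A(t) / Σ[A(t)·baseline(t)], and likewise for b

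The reported Arm 1 : Arm 2 ratio is a/b. With a true ratio of 1.0:

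| Transplant days, Arm 1 / Arm 2 | Late rate 0.3 | 0.5 | 1.0 | 2.0 |
|---|---|---|---|---|
| 0-180 / 0-365 | 0.71 | 0.75 | 0.83 | 0.91 |
| 0-365 / 0-365 | 0.98 | 0.98 | 0.99 | 0.99 |
| 0-120 / 0-120 | 1.00 | 1.00 | 1.00 | 1.00 |
| 120-365 / 0-120 | 2.51 | 2.20 | 1.76 | 1.38 |

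With the rate flat at 6.22 per year, every row is 1.00. The shift therefore needs both a falling rate and different timing.

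If Arm 1 truly had 30% more events, the first row's windows would give 0.97 (late rate 0.5) or 1.07 (late rate 1.0).

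**Transplant versus waiting.** With late and waitlist rates both 1.0, the true ratio is 6.2 in the first 30 days and 1.0 afterwards. The single Arm 1 ratio is 1.63 if Arm 1 is transplanted over days 0-60 and Arm 2 over days 180-365. It is 3.04 if Arm 1 is transplanted over days 120-365 and Arm 2 over days 0-120.

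**Clock from transplant.** With post-transplant person-time only and a late rate of 1.0, the ratio is 1.00 when the truth is 1.0 and 1.50 when it is 1.5, in all six timing scenarios tried. Splitting at day 30 on the enrolment clock also returns the true ratio in both periods.

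**Part 6, crude rates, identical timing over days 0-365.** Mean Arm 2 follow-up after transplant is the average of max(365 - u, 168) over u = 0 to 364, which is 221.4 days, against 365 in Arm 1. At a late rate of 0.5:

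- Arm 1: (0.511 + 0.5 × 335/365.25) / (365/365.25) = 0.970/0.999 = 0.97 per year
- Arm 2: (0.511 + 0.5 × 191.4/365.25) / (221.4/365.25) = 0.773/0.606 = 1.275 per year
- Ratio: 0.97/1.275 = 0.76

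For late rates of 0.3, 0.5, 1.0 and 2.0 the crude ratio is 0.71, 0.76, 0.84 and 0.91. With both arms transplanted over days 0-120 the shift is smaller: 0.91 to 0.97 for late rates of 0.5 to 2.0.

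**The case against.** The strongest reply is that the SAP is a draft summary with one short entry per analysis and never says that time runs from enrolment. A time-dependent arm does not by itself fix the origin, and with a transplant clock the problem disappears. That stands to this extent: the defect is an unstated scale, not a proven wrong one. But one model for all patients with a switching arm reads most naturally as starting before transplant.

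Second, the timing windows are assumed. Arm 1 closure runs on calendar time, whereas the bias needs a difference in time since enrolment. The two are linked, because enrolment stops at the 30th transplant and later transplants come only from patients already waiting. The link may be weak. A simulation of the closure rule (90 enrolled, entry staggered over 3 to 12 months, assumed transplant hazards) gave equal-risk ratios of 0.71-0.93, 0.79-0.95 and 0.89-0.97 at late rates of 0.5, 1.0 and 2.0. The direction held in those runs, but the size was often small, and with about 16 to 30 transplanted Arm 2 patients sampling error is as large as most of these shifts.

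Third, Part 15 is one secondary analysis. Arm 1 safety also rests on treatment-emergent events, laboratory data, graft outcomes and the post-transplant logistic regression (Protocol Sections 8.1.4 to 8.1.7). A reader might infer that the whole safety conclusion would be an artefact of the time scale; the documents do not support that.

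Treating arm as time-dependent is itself sound, since it keeps waiting time out of the post-transplant arms.

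**Conclusion.** The point holds in a limited form. If Parts 7 and 15 run from enrolment, and if event rates fall after the first month, the Arm 1 versus 2A/2B ratio mixes risk with transplant timing. Under equal risk it is about 0.71 to 0.91 with Arm 1 transplanted over months 0-6 and Arm 2 over months 0-12, 0.98 to 1.00 with the same timing, and above 1 with Arm 1 later. Only the 40% figure comes from the documents. The later rate, the waitlist rate and the timing are assumptions, so neither size nor direction is certain.

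Four stronger readings should be resisted:

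- **That the ratio reflects timing and not risk.** It reflects both: with a true ratio of 1.5 and matched timing, the model returns 1.47 to 1.50.
- **That the model fits one rate per arm.** The baseline is free; it is the ratio that is constant.
- **That unequal follow-up drives Parts 7 and 15.** With matched timing the ratio stays at 0.98 to 1.00. Follow-up length matters for the crude Part 6 rates, where it alone gives 0.71 to 0.91 with transplants spread over the first year.
- **That the transplant-versus-waiting ratio has the wrong sign for most of follow-up.** That requires a late rate below the waitlist rate, and neither is documented.

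**What to change.** **Parts 7 and 15:**
- State the time origin and the reference state.
- Compare Arm 1 with 2A + 2B1-2B4 on post-transplant person-time only, with time since transplant as the time scale and its own baseline rate.
- For transplant versus waiting, report separate rate ratios for days 0-30 and after day 30 post-transplant.
- No 24-week cut is needed in the Arm 1 versus Arm 2 model: once the clock is reset, the risk sets handle unequal follow-up and later events are kept.

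**Part 6:** report crude post-transplant rates over a common window, for example 0-24 weeks, or split them at day 30.

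**Cost:** a few lines of SAP text and code, and no new data. If the common window is used, events after it leave the crude Part 6 comparison but can still be listed.

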5.0 Investigational Plan

5.1 Overall Study Design, Rationale and Plan: Description

This is a Phase 4, open-label, multi-center, 2-arm study with the primary objective of evaluating the efficacy (SVR12) and safety of the fixed-dose combination tablets of glecaprevir/pibrentasvir (G/P) in HCV-negative subjects who receive a kidney transplant from an HCV RNA-positive deceased kidney donor. Among 90 subjects consented for trial participation, 30 subjects at up to 7 sites are planned to receive an HCV RNA-positive kidney and will be enrolled into a post-transplant treatment arm (Arm 1) receiving open-label G/P for 8 weeks post-transplant. The remaining consented patients who do not receive a study eligible kidney from an HCV RNA-positive donor will be followed in Arm 2 for the minimum duration of 1 year post-enrollment (Arm 2B and 2C), or 24 weeks post-transplant, whichever is longer (Arm 2A). These Arm 2 subjects include patients who do

not receive a kidney transplant (Arm 2C) or who receive a study eligible kidney from an HCV RNA-negative/HCV Ab-positive donor (Arm2A), or from a standard of care donor (Arm 2B). Follow-up for study participants who receive a kidney transplant at a non-study site (Arm 2B5) will be censored at transplantation.

For subjects of Arm 1 of the study, the first dose of G/P will be given as early as 3 days post-transplant. Patients must be out of the ICU, able to eat and drink, take oral medications, and G/P treatment can be safely initiated orally as judged by the site investigator.

Enrolled subjects will be activated in the United Network for Organ Sharing (UNOS) allocation system as eligible for kidney allograft offers from deceased donors that are HCV RNA-positive, HCV Ab-positive, or both.

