8.1 Statistical and Analytical Plans

The data analysis will be generated using SAS version 9.4 or higher for windows and/or STATA software version 14.0 or higher (StataCorp LP, College Station, TX). SAS Institute Inc. SAS and all other SAS Institute Inc. product or service names are registered trademarks or trademarks of SAS Institute Inc., Cary, NC, USA. All statistical tests (if applicable) and confidence intervals will be two-sided with an alpha level of 0.05.

Descriptive statistics will be provided, such as the number of observations (N), mean, and standard deviation (SD) for continuous variables and counts and percentages for discrete variables.

The efficacy and safety of the “reactive” G/P treatment of patients who become HCV RNA-positive after receiving a kidney from a study eligible HCV RNA-negative/HCV Ab-positive donor in Arm 2A are not an objective of this study, and they are not included in assessments of efficacy or safety described below. The time to transplant and clinical outcomes and data post-transplant from patients in Arm 2A are included in those secondary endpoints.

The primary analysis will occur after all recipients of HCV RNA-positive kidneys in Arm 1 have completed post-treatment week 12 visit (corresponding to SVR₁₂ data collection) or prematurely discontinued study. The primary analysis of SVR₁₂ will be performed on the intention-to-treat (ITT) population defined as all enrolled subjects who received a study eligible HCV RNA-positive kidney and received at least one dose of G/P according to actual treatment received (Arm 1).

No data will be imputed for any efficacy or safety analysis except for analyses of SVR endpoints (HCV RNA data). HCV RNA values will be selected for the analyses of all SVR endpoints (e.g., SVR₄ and SVR₁₂, SVR₂₄) based on defined visit windows. A backward imputation method will be used to impute missing responses for SVR analyses. Additional details of analyses to be performed will be specified in the Statistical Analysis Plan.

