Clinical outcomes post-transplant will include death, graft failure, acute allograft rejection, delayed graft function, ALT elevation > 5 times the upper limit of normal, and SAEs. In addition, HCV-infection related events of fibrosing cholestatic hepatitis and extrahepatic manifestations of HCV infection collected for Arm 1 subjects and only for Arm 2A subjects who develop HCV viremia will also count as clinical outcomes. The number and percentage of subjects with each and any clinical outcomes will be summarized for those who receive an HCV RNA-positive kidney (Arm 1) versus Arm 2 subjects combined and broken down (2A and 2B) as applicable. The difference in the overall percentage of subjects with clinical outcomes post-transplant in Arm 1 vs Arm 2A + 2B will be assessed by logistic regression with Arm as a factor and including appropriate covariates to adjust for possible differences between Arms including waiting list priority, blood group,

geographic region and sensitization, as appropriate given sample size and other statistical considerations. In addition, to include any clinical outcomes due to being treated with G/P, another summary of clinical outcomes post-transplant will include any study drug (G/P) related severe treatment emergent adverse events for Arm 1 subjects, and another will include events of treatment emergent Grade ≥ 3 laboratory values and related severe treatment emergent adverse events as clinical outcomes for Arm 1 subjects.

Analyses of the eGFR outcome will be calculated eGFR using the 4-variable MDRD equation. Mean (SD) eGFR will be summarized at appropriate visits and compared between Arms. Specifically, mean eGFR at 24 weeks/6-months post-transplant and 1 year post transplant will be compared between Arm 1 transplant recipients and the combined group of Arm 2A and 2B transplant recipients (2B1-2B4). As a secondary approach, mean eGFR at 24 weeks/6-months post-transplant will be compared between Arm 1 recipients and Arm 2A and 2B kidney recipients limited to those 2A and 2B recipients who did not develop HCV infection.

We will also compare estimated proteinuria between Arms 1 and 2A, including a count of individuals with >1000 mg/day estimated proteinuria. Proteinuria will be estimated using spot protein:Cr ratio.

An exploratory analysis will summarize the number and percentage of subjects with clinical outcomes post kidney transplant for the subgroups of Arm 2B.

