There may also be a small risk of developing Focal and Segmental Glomerulosclerosis (FSGS) after receiving a kidney from HCV-RNA-positive donor and/or being treated for HCV after transplantation. However, this condition can also develop in patients who do not have HCV. There have been case reports of FSGS among patients receiving treatment for HCV after kidney and liver transplantation. It is possible that such cases were related to HCV treatment. After transplant, we will monitor all patients for FSGS and similar conditions by checking proteinuria at every study visit post-transplant.

There may also be a small risk of developing symptoms of acute HCV infection, or extrahepatic manifestations of HCV infection if the start of HCV treatment is delayed. After transplant, we will monitor all patients and will initiate HCV treatment as early as feasible on or after day 3 post-transplant.

Taking part in a research study may cause psychological distress or excess worry. A subject may experience discomfort if asked questions about the subject's medical history that the subject deems to be private.

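### SAP Part 17 tests proteinuria only as a yes/no response, so the plan has no between-arm estimate of the proteinuria level that protocol 8.1.4 sets out to compare

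*SAP*

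**What the plan says.** Protocol section 8.1.4 states: "We will also compare estimated proteinuria between Arms 1 and 2A, including a count of individuals with >1000 mg/day estimated proteinuria". It adds: "Proteinuria will be estimated using spot protein:Cr ratio". The threshold count is thus one item within a wider comparison of a continuous quantity. No test is named and no power is claimed.

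Protocol section 9.4.1 gives the clinical reason for measuring it: "we will monitor all patients for FSGS and similar conditions by checking proteinuria at every study visit post-transplant".

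SAP Part 17 covers proteinuria for Arms 1, 2A and 2B. Its whole specification is "Binary response; logistic regression". It states no cut-point, no visit and no way to combine repeated ratios. The row above it, Part 16, treats the other allograft function measure, eGFR, as a repeated continuous response: "Linear mixed model, to account for clustering by patient". Note (a) applies to every row: "Each of the above-listed analyses will be accompanied by appropriate summary statistics (e.g., mean, median, IQR, etc".

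**The concern.** The SAP is the later document, and it gives no inferential counterpart to the protocol's comparison of estimated proteinuria. Summary statistics by arm will be shown, but there will be no effect estimate, confidence interval or test for the level. Nothing explains why proteinuria is cut when eGFR is not.

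The groups are small and the only threshold in the documents, 1000 mg/day, may lie far out in the tail. A general upward shift of proteinuria in Arm 1 could then pass as no difference, although the collected ratios might show it. Proteinuria is the outcome tied to glomerular injury after an HCV RNA-positive kidney, and the eGFR analysis does not replace it in that role.

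**Working it through.** **Inputs from the documents.** Arm 1: "30 subjects at up to 7 sites are planned to receive an HCV RNA-positive kidney" (protocol 5.1). Arm 2A: at most 20 (protocol 5.1). Comparators in Arms 2A and 2B together: protocol 8.2 expects at least 40 transplants among 90 enrolled, so 40 − 30 = 10 at the low end and 90 − 30 = 60 if everyone is transplanted. Error rate: "All statistical tests (if applicable) and confidence intervals will be two-sided with an alpha level of 0.05" (protocol 8.1). There is no planned power figure for proteinuria to reproduce.

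**Assumptions, not in the documents.** The ratio is log-normal, comparator median 150 or 250 mg/g, SD of the log 0.8 or 1.0. A ratio of 1000 mg/g is read as 1000 mg/day. There is one complete measurement per recipient.

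**Step 1: events under a general doubling in Arm 1.** The share above the cut is 1 − Φ[(ln 1000 − ln median)/SD].
- Median 150, SD 0.8: comparators 1 − Φ(2.37) = 0.9%, so 20 × 0.0089 = 0.18 expected events. Arm 1 (median 300): 1 − Φ(1.505) = 6.6%, so 30 × 0.066 = 2.0.
- Median 250, SD 1.0: comparators 1 − Φ(1.386) = 8.3%, so 1.7 events. Arm 1 (median 500): 1 − Φ(0.693) = 24.4%, so 7.3.

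The chance that 20 comparators have no event is (1 − 0.0089)^20 = 0.84 in the first case and (1 − 0.083)^20 = 0.18 in the second. With no comparator event, an ordinary logistic odds ratio cannot be estimated.

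**Step 2: power for that doubling, 30 versus 20** (20,000 simulated trials per row; Welch t-test on the log ratio against the likelihood-ratio test of the logistic model and Fisher's exact test, cut at 1000).

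| Median, SD | Log scale | Logistic LR | Fisher | LR power ÷ log-scale power |
|---|---|---|---|---|
| 150, 0.8 | 83% | 11% | 0% | 0.110/0.829 = 13% |
| 150, 1.0 | 65% | 26% | 3% | 0.255/0.653 = 39% |
| 250, 0.8 | 84% | 45% | 20% | 0.454/0.836 = 54% |
| 250, 1.0 | 65% | 37% | 23% | 0.365/0.645 = 57% |

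With 40 comparators the ranges are 81–94% (log scale) and 24–58% (logistic). With 10 they are 43–60% and 0–27%. With a cut at 300 or 500 mg/g, median 200 and 20–40 comparators, the log scale gains about 13–25 points.

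**Step 3: analytic check.** For a small shift, the efficiency of a split relative to the full scale is φ(c)²/[p(1 − p)], where p is the share of comparators above the cut and c the matching normal quantile. It is 0.64 at p = 50%, 0.49 at 20%, 0.34 at 10% and 0.22 at 5%. With 30 versus 60 and a shift of 0.8 SD, power is 95% on the full scale and 79%, 70% and 59% for splits at p = 20%, 10% and 5%.

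**Step 4: a different signal.** Suppose 20% of Arm 1 has a median of 2500 mg/g and the rest match the comparators (median 200, SD of the log 0.9).

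| Log-SD in the subset | Comparators | Log-scale t-test | Logistic LR, cut 1000 | Fisher, cut 1000 |
|---|---|---|---|---|
| 0.5 | 20 | 34% | 57% | 32% |
| 0.5 | 40 | 42% | 73% | 63% |
| 0.5 | 60 | 46% | 78% | 74% |
| 0.9 | 20 | 33% | 50% | 23% |
| 0.9 | 40 | 40% | 64% | 51% |

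With 40 or more comparators the split is the better test. With 20, the likelihood-ratio test favours the split, but with so few events it is unreliable. Fisher's test roughly ties with the t-test or falls below it.

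**The case against.** The strongest reply is that the binary analysis suits the harm in question. Protocol 9.4.1 describes a small risk of FSGS, and the earlier single-arm trial described in protocol section 3.0 saw it in one of ten recipients. That is heavy proteinuria in a few patients, not a doubling in all, and step 4 shows the split can then do better. This stands. It is a reason to keep the threshold comparison, but not to have it alone.

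A reader might infer that the SAP discards the protocol's proteinuria comparison. The documents do not support that: the count above 1000 mg/day is the protocol's own item, and note (a) keeps means, medians and IQRs. What is missing is an estimate and interval for the difference in level.

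The numerical model also has limits. Part 17 names no cut, so 1000 is borrowed from the protocol. Its comparator is Arms 2A and 2B, so 20 is not its ceiling. The simulation uses one complete measurement, not a mixed model. For standard-of-care recipients, protocol 5.1.10 obtains proteinuria only where the medical record holds it. This last point affects which comparator the new analysis should use.

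Finally, the study is for feasibility and preliminary data (protocol 8.2), objective 3 is framed as descriptive, and the SAP is a draft summary. These points limit the importance, but a draft is also easy to amend.

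**Conclusion.** The point holds in this form: Part 17 contains only a binary model for a continuous measure, and the between-arm comparison of the level planned in protocol 8.1.4 has no inferential counterpart in the SAP.

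Its size is conditional. For a general doubling, a cut at 1000 and 30 versus 20, power is about 65–84% on the log scale against 11–45% for the logistic test. All distributional inputs are assumed.

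Two stronger readings should be resisted. One is that the SAP loses most of the power. In two of the four settings in step 2 the logistic test keeps more than half, larger groups or lower cuts narrow the gap, and a subset signal can reverse it. The other is that a renal signal as such is lost. eGFR stays continuous in Part 16, and patient-level monitoring does not depend on Part 17. This is a worthwhile, inexpensive improvement to a secondary safety analysis.

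**What to change.** Amend SAP Part 17 as follows.

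- Add a linear mixed model of the log protein:creatinine ratio, in the form of Part 16, with arm and time since transplant. Report the Arm 1 to comparator geometric mean ratio with its 95% CI.
- Use Arm 2A, whose ratios are scheduled by the protocol, as the main comparator, in line with protocol 8.1.4. Show Arms 2A and 2B combined as supportive, because the 2B values are not collected on a schedule.
- Keep the binary comparison. Define it at the protocol's threshold of more than 1000 mg/day, state the visit or window and how repeated values are combined, and use an exact or penalised logistic method because events may be few.

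The cost is SAP wording and one more secondary result to report, with a sentence explaining the geometric mean ratio. No new samples or visits are needed.
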